6.1.11 Derived data

The derived data are variables which are calculated from the raw data in the CRF and not included in the database (e.g.: Age, BMI). The formula used for derived data and the strategy for missing data are provided in Section 12.1.

6.1.12 Visit windows

The screening visit can occur anytime within 8 weeks before the injection day (Day 0).

The first follow-up visit (phone call) should occur within 24 hours after the injection. The second follow-up visit should occur 30 days after the injection with a window of 3 days, i.e. the visit has to be performed between the 27th and the 33rd day from the ^{99m}Tc-rhAnnexin V-128 administration.

6.1.13 Rules and data formats

Data will be presented using an appropriate number of decimal places (i.e. the number of decimal places used does not imply undue precision). Raw data will be presented to the number of decimal places collected, and derived data will be presented to an appropriate number of decimal places. The appropriate number of decimal places will be determined by general practice, mathematical rationale or scientific rationale (e.g. age should be presented in whole numbers).

For summary statistics, the following will be presented: number of non-missing values (n), number of missing values, arithmetic mean, standard deviation, median, the IQR (first quartile, third quartile), the range (minimum, maximum) and, only if appropriate, 95% 2-sided confidence interval.

Mean, standard deviation, first quartile, median, third quartile and confidence interval values will be rounded to one more decimal place than the raw data whereas minimum and maximum will be reported with the same precision as the raw data.

Percentages will be reported to one decimal place. Percentages will be calculated using a denominator of all subjects in a specified population. The denominator will be specified in a footnote to the tables for clarification if necessary.

p-values will be reported to four decimal places (e.g., p=0.0037), after rounding; p-values which are less than 0.0001 will be presented as "<0.0001".

Version: 01 Page: **31 of 167**

All text fields must be left justified and numeric or numeric with some text specification (e.g., not done, unknown, <4.5, ...) must be decimal justified. Dates will be presented in the format [dd/mm/yyyy] and times in the format [hh:mm] using 24-hour clock scale.

6.1.14 Pooling of centres

Not applicable.

6.1.15 Interim analysis

No formal interim analysis will be done; however the DMC will analyse Planar and SPECT/CT images of the first 15 patients and of the first 5 controls in order to determine the feasibility of imaging apoptotic activity in carotid atherosclerotic plaques of asymptomatic or symptomatic with TIA patients with significant carotid disease, by using ^{99m}Tc-rhAnnexin V-128 imaging, and to report the prevalence of abnormal ^{99m}Tc-rhAnnexin V-128 scans.

6.1.16 Role of independent data monitoring committee (DMC) / interim data review committee

The Data Monitoring Committee (DMC) consists of investigators and Sponsor representatives, as well as external persons such as independent experts, if deemed necessary by the Sponsor. The main function of the committee will be to review and evaluate the images of the first 15 patients and of the first 5 healthy participants in terms of image quality, carotid target uptake and clinical relevance of the study product. The DMC will also review the safety data. The frequency of abnormal carotid scans will be determined in the participant and control groups. The study will be terminated if there is a low frequency of positive scans in the carotid participant group or high frequency of positive scans in the control group.

The DMC will promptly give recommendations to continue or terminate the study. The DMC report will be prepared by the Sponsor and sent to the REB and regulatory authorities as required. Preliminary results can be used by the Sponsor for publication purpose, before the end of the main trial.

6.1.17 Covariates and analysis of subgroups

The analysis on the efficacy endpoints will be performed on the two groups of enrolled subjects (patients and control group). Patient group will also be divided into two groups (normal and abnormal) depending on imaging results (negative or positive).

Confidential

Version: 01 Page: **32 of 167**

If deemed relevant some additional analysis might be conducted to explore the impact of clinically relevant covariates such as the level of carotid stenosis (as determined by ultrasound), history of TIA and any other relevant factors on the results.

6.1.18 Sensitivity analysis

Not Applicable.

6.1.19 Multiplicity

As stated in the protocol, no adjustments will be made for multiplicity.

6.1.20 Significance testing and estimation

All statistical tests will be two-sided at the 5% level of significance.

7 COMPUTER SYSTEMS, SOFTWARE AND VALIDATION OF PROGRAMS

7.1 Hardware

The statistical analysis will be performed using Dell personal computer with Windows 7 professional (64 bit) as operating system.

7.2 Software

All tables, listings and figures will be produced and statistical analysis performed using SAS version 9.4. All output will be in Word format.

7.3 Validation programs

An Independent Statistician is responsible for reviewing each project program and output associated with the deliverable product. Program logs are reviewed for logical, syntax and fatal errors. The review in SAS includes, but is not limited to, all ERRORS, WARNINGS, NOTES, and variables check. Program logs are also reviewed for accurate and consistent variable and observation counts following each procedure and data step.

The Independent Statistician is also responsible for checking and reviewing the work produced using whatever method he/she feels is appropriate (e.g. SAS commands review, hand calculation, etc.) to reassure of the quality of the output.

Outputs are reviewed for typographical errors, misspellings and nonsensical values or results and to check the consistency with the reporting and analysis plan. Outputs are cross-checked against each other for accuracy and consistency. For statistical tables, listings, and figures, this procedure includes comparison of subject group numbers, counts of subjects at each observation point, and consistency of results for variables between outputs.

Findings of the quality control reviews are communicated to the party responsible for making necessary changes. The programs will be retested after modifications.

After final review, and when no further changes are required to produce the deliverables, the Independent Statistician needs to complete and sign the SAS Outputs, to indicate that he has successfully performed all of his responsibilities.

Confidential

Version: 01 Page: **34 of 167**

8 CHANGES FROM PROTOCOL

No changes from the protocol were made.

Statistical Analysis Plan ANNEXIN 04 Confidential

Version: 01

Page: **35 of 167**

9 REFERENCES

Not applicable.

Version: 01 Page: **36 of 167**

10 DATA PRESENTATION

Data listings are presented for all screened subjects.

Footnotes should be used to clarify ambiguities (e.g.: the denominator used to calculate a percentage or notes for the programmer). If the number of footnotes is high, they could be presented only in the last page, with on each page the following footnote "See last page for listing notes". The order of the footnotes for key symbols (*, ~) will be in the order that they appear in the listing.

10.1 Listings index

16.2 SUBJECT DATA LISTINGS

16.2.1 Discontinued subjects

Listing 16.2.1.1: Subject Disposition – All Subjects

Listing 16.2.1.2: Subject Disposition – Study Withdrawals

Listing 16.2.1.3: Inclusion Criteria

Listing 16.2.1.4: Exclusion Criteria

Listing 16.2.1.5: Screening Failures

16.2.2 Protocol deviations

Listing 16.2.2: Protocol Deviations and Reasons for Exclusion from the Study

Populations

16.2.3 Subjects excluded from the efficacy analysis

Not applicable

16.2.4 Demographic data

Listing 16.2.4.1: Demographics

Listing 16.2.4.2: Carotid Ultrasound

Listing 16.2.4.3: Medical History and Associated Pathologies

Listing 16.2.4.4: Prior and Concomitant Medications

16.2.5 Compliance and/or drug concentration data

Listing 16.2.5.1: Study Drug Administration and Extent of Subject Exposure

16.2.6 Individual efficacy response data

Listing 16.2.6.1: Carotid and Aorta Imaging Assessment

Confidential

Version: 01 Page: **37 of 167**

Listing 16.2.6.2: Carotid and Aorta Imaging Assessment – Uptake – Data Recorded

on DMC Assessement Form

16.2.7 Adverse event listings (each subject)

Listing 16.2.7.1: All Adverse Events

Listing 16.2.7.2: Serious Adverse Events

Listing 16.2.7.3: Adverse Events Leading to Withdrawal

Listing 16.2.7.4: Adverse Events with Outcome Death

16.2.8 Listing of individual laboratory measurements by subject

Listing 16.2.8.1: Hematology

Listing 16.2.8.2: Blood Chemistry

Listing 16.2.8.3: Urinalysis

Listing 16.2.8.4: Immunogenicity

16.2.9 Listing of other safety data

Listing 16.2.9.1: Pregnancy Test

Listing 16.2.9.2: Physical Examination

Listing 16.2.9.3: Vital Signs

10.2 Listing templates

Listing templates are provided in Appendix 11.1. The listings will be presented in landscape, in a fixed font (Arial) with a minimum size as 8.

10.3 Tables index

14. TABLES, FIGURES AND GRAPHS

14.1 DEMOGRAPHIC DATA

Table 14.1.1: Subject Disposition

Table 14.1.2: Analysis Populations

Table 14.1.3: Protocol Deviations

Table 14.1.4.1: Demographics – FAS Population

Table 14.1.5.1: Carotid Ultrasound – FAS Population

Confidential

Page: **38 of 167**

Table	14.1.6.1:	Medical History and Associated Pathologies – Safety Population
Table	14.1.7.1:	Prior Medications or Non-Drug Tharapies – Safety Population
Table	14.1.7.2:	Prior and Concomitant Medications or Non-Drug Therapies – Safety Population
Table	14.1.8.1:	Study Drug Administration – Safety Population
14.2 EFFICACY	DATA	
Table	14.2.1.1:	Carotid and Aorta Imaging Assessment – Prevalence of Positive Scans – FAS Population
Table	14.2.1.2:	Carotid and Aorta Imaging Assessment – Prevalence of Positive Scans – PP Population
Table	14.2.1.3:	Patient Carotid and Aorta Imaging Assessment – Comparison between time point – FAS Population
Table	14.2.1.4:	Left Carotid Uptake Imaging Assessment – Target to Background Ratio (TBR) – FAS Population
Table	14.2.1.5:	Right Carotid Uptake Imaging Assessment – Target to Background Ratio (TBR) – FAS Population
Table	14.2.1.6:	Thoracic Aorta Uptake Imaging Assessment – Target to Background Ratio (TBR) – FAS Population
Table	14.2.1.7:	Abdominal Aorta Uptake Imaging Assessment – Target to Background Ratio (TBR) – FAS Population
Table	14.2.1.8:	Aortic Arch Uptake Imaging Assessment – Target to Background Ratio (TBR) – FAS Population
Table	14.2.1.9:	Left Carotid Uptake Imaging Assessment by ultrasound grade of plaque echolucency/echogenicity – Target to Background Ratio (TBR) – Patients - FAS Population
Table	14.2.1.10:	Right Carotid Uptake Imaging Assessment by ultrasound grade of plaque echolucency/echogenicity – Target to Background Ratio (TBR) – Patients - FAS Population

Version: 01

14.3 SAFETY DATA

14.3.1 Displays of Adverse Events

Table 14.3.1.1: Overall Summary of Adverse Events – Safety Population

Confidential

Page: 39 of 167

Table 14.3.1.2:	Number (%) of Subjects Reporting Treatment Emergent Adverse
	Events by Primary System Organ Class and Preferred Term -
	Safety Population
Table 14.3.1.3:	Number (%) of Subjects Reporting Treatment Emergent Adverse
	Events by Severity – Safety Population
Table 14.3.1.4:	Number (%) of Subjects Reporting Adverse Drug Reactions by
	Severity – Safety Population
Table 14.3.1.5:	Number (%) of Subjects Reporting Treatment Emergent Serious
	Adverse Events by Primary System Organ Class and Preferred
	Term – Safety Population
Table 14.3.1.6:	Number (%) of Subjects Reporting Treatment Emergent Serious
	Adverse Events by Severity – Safety Population
Table 14.3.1.7:	Number (%) of Subjects Reporting Serious Adverse Drug Reactions
	by Severity – Safety Population

14.3.2 Listings of Deaths, Other Serious and Significant Adverse Events

Version: 01

Table 14.3.2.1: Listing of Adverse Events with Outcome Death – Safety Population

Table 14.3.2.2: Listing of Serious Adverse Events – Safety Population

14.3.3 Narratives of Deaths, Other Serious and Certain Other Significant Adverse Events

Only raw narratives will be presented in this section if any.

14.3.4 Abnormal Laboratory Value Listing (each patient)

Only patients with clinically significant abnormal laboratory value(s) will be presented in this section if any.

Table 14.3.4: Abnormal Laboratory Value Listing (Each Patient) – Safety Population

14.3.5 Laboratory Measurements

Table 14.3.5.1: Hematology – Safety Population

Table 14.3.5.2: Blood Chemistry – Safety Population

Table 14.3.5.3: Urinalysis – Safety Population

14.3.6 Other Safety Data

Table 14.3.6.1: Vital Signs – Safety Population

Version: 01 Page: **40 of 167**

10.4 Table templates

Table templates are provided for each unique table in Appendix 11.2. The tables will be presented in landscape, in a fixed font (arial) with a minimum size as 8.

All tables, in table number order, must be presented in a single Word file.

10.5 Figures index

14. TABLES, FIGURES AND GRAPHS

14.2 EFFICACY DATA

Figure 14.2.1.1:	Left Carotid Target to Background Ratio (TBR) Imaging Assessment - Patients – Carotid with Stenosis ≥ 50% – FAS Population - 60 mins after IP injection
Figure 14.2.1.2:	Left Carotid Target to Background Ratio (TBR) Imaging Assessment - Patients – Carotid with Stenosis ≥ 50% – FAS Population - 120 mins after IP injection
Figure 14.2.1.3:	Right Carotid Target to Background Ratio (TBR) Imaging Assessment - Patients - Carotid with Stenosis ≥ 50% - FAS Population 60 mins after IP injection
Figure 14.2.1.4:	Right Carotid Target to Background Ratio (TBR) Imaging Assessment - Patients - Carotid with Stenosis ≥ 50% - FAS Population - 120 mins after IP injection
Figure 14.2.1.5:	Scatterplot between Left and Right Carotid and Thoracic Aorta Target to Background Ratio (TBR) – Patients – FAS Population - 60 mins after IP injection
Figure 14.2.1.6:	Scatterplot between Left and Right Carotid and Thoracic Aorta Target to Background Ratio (TBR) – Patients – FAS Population - 120 mins after IP injection
Figure 14.2.1.7:	Scatterplot between Left and Right Carotid and Abdominal Aorta Target to Background Ratio (TBR) – Patients – FAS Population - 60 mins after IP injection

Page: 41 of 167

Figure 14.2.1.8:	Scatterplot between Left and Right Carotid and Abdominal Aorta
	Target to Background Ratio (TBR) - Patients - FAS Population -
	120 mins after IP injection
Figure 14.2.1.9:	Scatterplot between Left and Right Carotid and Aortic Arch Target
	to Background Ratio (TBR) – Patients – FAS Population - 60 mins
	after IP injection
Figure 14.2.1.10:	Scatterplot between Left and Right Carotid and Aortic Arch Target
	to Background Ratio (TBR) – Patients – FAS Population - 120 mins

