Reconstruction will be done using iterative reconstruction incorporating CT-based attenuation correction and dual-energy-window scatter correction. Planar and SPECT images of the carotid arteries and thoracic and abdominal aorta will be acquired at 1 and 2 hours post-injection. Acquired images will be stored for off-line analysis using a Hermes Gold workstation (Hermes Medical Solutions). Volumes-of-interest (VOIs) will be placed over the carotids and the thoracic and abdominal aortic sections to determine image counts from the attenuation and scatter corrected images. A ^{99m}Tc source of known activity will be imaged and used to determine the imaging system calibration factor for converting reconstructed image counts into an activity concentration (MBq/cc or % injected dose/gram).

A normal database of carotid and aortic uptake will be determined from 10 control participants and used to identify abnormal uptake in carotid artery disease participants.

Inter and intra-observer variability will be determined by repeated analysis of the images of 20 participants. Two observers will carry out the assessment of inter-observer variability. Images will be anonymized prior to analysis and observers will be blinded to all clinical data.

10.4 ^{99m}Tc -rhAnnexin V-128 Radiation Risk Assessment

Participants will receive radiation from 1) ^{99m}Tc -rhAnnexin V-128 (350 MBq) for a dose of 2.2 mSv (7.7 ± 0.8 uSv/MBq) and 2) the CT scan for attenuation correction for a dose of 1.8 mSv. Total dose for ^{99m}Tc -rhAnnexin V-128 and CT components will be 4.0 mSv.

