4.1.2.1 Secondary hypotheses

- ^{99m}Tc-rhAnnexin V-128 uptake will be increased in plaque with greater echogenicity.
- 99mTc-rhAnnexin V-128 uptake will be decreased in plaque with greater echolucency.
- 99mTc-rhAnnexin V-128 imaging can be used to detect apoptosis in the aorta in asymptomatic patients with at least one 50% carotid stenosis as defined by ultrasounds.
- Aortic uptake of ^{99m}Tc-rhAnnexin V-128 will be correlated with carotid uptake of ^{99m}Tc-rhAnnexin V-128.

Version: 01 Page: **15 of 167**

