Reconstruction will be done using iterative reconstruction incorporating CT-based attenuation correction and dual-energy-window scatter correction. SPECT images of the carotid arteries and thoracic and abdominal aorta will be acquired at 1 and 2 hours post-injection. Acquired images will be stored for off-line analysis using a Hermes Gold workstation (Hermes Medical Solutions). Volumes-of-interest (VOIs) will be placed over the carotids and the thoracic and abdominal aortic sections to determine image counts from the attenuation and scatter corrected images. A ^{99m}Tc source of known activity will be imaged and used to determine the imaging system calibration factor for converting reconstructed image counts into an activity concentration (MBq/cc or % injected dose/gram).

A normal database of carotid and aortic uptake will be determined from 10 control participants and used to identify abnormal uptake in carotid artery disease participants.

Inter and intra-observer variability will be determined by repeated analysis of the images of 20 participants. Two observers will carry out the assessment of inter-observer variability. Images will be anonymized prior to analysis and observers will be blinded to all clinical data.

4.3.3.4 99mTc-rhAnnexin V-128 Radiation Risk Assessment

Participants will receive radiation from 1) ^{99m}Tc-rhAnnexin V-128 (350 MBq) for a dose of 2.2 mSv (7.7 ± 0.8 uSv/MBq) and 2) the CT scan for attenuation correction for a dose of 1.8 mSv. Total dose for ^{99m}Tc-rhAnnexin V-128 and CT components will be 4.0 mSv.

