6.1.2.3 Secondary endpoints

The secondary endpoints of Phase II and the related statistical analysis are:

- Descriptive statistics of ^{99m}Tc-rhAnnexin V-128 uptake in patients vs control participants will be presented by areas of interest (left carotid, right carotid, thoracic aorta, abdominal aorta and aortic arch) and by time points to assess the background uptake profile and the pathologic profile. Comparison of uptake in patients vs controls at each timepoint will be explored by the most appropriate test i.e. two sample t-test.
- The relationship between carotid uptake (separately for left and right) and ultrasound grade of plaque echolucency/echogenicity (1 echolucent, 2 predominantly echolucent, 3 predominantly echogenic, 4 echogenic) will be assessed for all patients using box plots and

Version: 01 Page: **26 of 167**

summaries of uptakes by the levels of echolucency/echogenicity for each time point. Only carotids with stenosis (defined as \geq 50% as per protocol) will be included in this analysis (i.e. a patient with only 1 carotid with stenosis \geq 50% will contribute data for that carotid uptake value and the associated plaque echolucency/echogenicity value for the same carotid, patients with stenosis in both carotids will contribute data on uptake and echolucency/echogenicity for each of their carotids).

Association between carotid and aortic uptake will be assessed for patients and controls, by time
point, using scatter plots. All carotids with ≥ 50% stenosis (as described above) will be included
in this plot, and different colours/symbols will be used for left and right carotid results. If further
investigation is considered appropriate, the correlation coefficients (Pearson's or Spearman's)
within left carotids and right carotids separately will be calculated.

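### The carotid–aorta association is planned only as TBR against TBR with an undefined denominator, so the figures alone cannot show whether uptake in the two vessels is related

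*SAP*

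**What the plan says.** The SAP's last secondary hypothesis (4.1.2.1) is that aortic uptake "will be correlated with carotid uptake of" the tracer. SAP 6.1.2.3 carries this forward: "Association between carotid and aortic uptake will be assessed for patients and controls", by time point and using scatter plots. Only carotids with at least 50% stenosis enter. If more is thought useful, "the correlation coefficients (Pearson's or Spearman's") "within left carotids and right carotids separately will be calculated".

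The imaging methods (Protocol 10.3, SAP 4.3.3.3) turn image counts into an activity concentration, MBq/cc or % injected dose per gram. The regions they name are these: "Volumes-of-interest (VOIs) will be placed over the carotids and the thoracic and abdominal aortic sections". No background or blood-pool region is mentioned.

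The outputs use another quantity. Figures 14.2.1.5 to 14.2.1.10 cover thoracic aorta, abdominal aorta and aortic arch at 60 and 120 minutes. Each puts a target to background ratio on both axes, as in "Scatterplot between Left and Right Carotid and Thoracic Aorta Target to Background Ratio (TBR"). The uptake summary tables are also in TBR. Listing 16.2.6.2 has five TBR columns, gives the sponsor as data source, and shows neither numerator nor denominator. The Protocol's abbreviation list spells TBR out, but neither document says what the background is or whether each vessel has its own.

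**The concern.** The question is about uptake and the display is about ratios. Suppose one background value per scan divides both the carotid and the aortic value. A participant with low background then has both ratios raised, and one with high background has both lowered. The points spread along a rising line even if the two vessels have nothing to do with each other.

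No uptake plot, table or listing is indexed, and the listing does not carry the background value. A reader of the report could not tell a vessel-to-vessel link from variation in the denominator, or find out whether the denominator is shared. Protocol 12.4 intends exploratory results of this kind to inform later confirmatory trials, so a false lead would carry forward.

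**Working it through.** **Inputs.** The only spread given is the Phase I neck uptake in 12 normals, 0.8 ± 0.27 %ID/g (Protocol 12.1, SAP 4.3.5), so CV = 0.27/0.8 = 0.34. Applying it to the carotid and the aorta in patients is an assumption. The documents give no background CV, so a range is used. Tests are two-sided at 5% (SAP 6.1.20).

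**The plan's own figure.** No figure is given for the correlation. The sample size that uses the same SD does reproduce. With 9 normals, 25 patients and a difference of 0.4, 0.4/(0.27 × √(1/9 + 1/25)) = 3.81. Normal-theory power is Φ(3.81 − 1.96) = 96.8%, and with the t distribution 95.9%, against a stated 95%.

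**Number of pairs.** Coefficients would be computed within each side, on stenosed carotids only, and eligibility needs stenosis in one carotid. A value of n=35 on one side needs every patient to be stenosed on that side. If each of the 35 had one stenosed carotid, split evenly, n would be about 35/2, or 18. Results are shown for 18, 25 and 35.

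**Shared background, everything independent.** For carotid C, aorta A and background B, the usual approximation to the correlation of C/B with A/B is

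r ≈ CVb² / √[(CVc² + CVb²)(CVa² + CVb²)].

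With CVc = CVa = 0.3375 and CVb = 0.20, this is 0.04/(0.04 + 0.114) = 0.26. Simulation with independent lognormal values (20,000 trials per setting, true association zero, Spearman) gives:

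| Background CV | Approximate r | Simulated mean r (n=35) | p<0.05, n=18 | n=25 | n=35 |
|---|---|---|---|---|---|
| 5% | 0.02 | 0.02 | 5% | 5% | 5% |
| 10% | 0.08 | 0.08 | 6% | 7% | 7% |
| 20% | 0.26 | 0.25 | 17% | 23% | 31% |
| 34% | 0.50 | 0.47 | 52% | 68% | 84% |

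In the same runs, correlating uptake itself gave mean r 0.00 and about 5%.

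**Separate backgrounds.** With an independent background for each vessel at CV 34% and n=35, the TBR correlation averages 0.00 and p<0.05 occurs in 4.7%.

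**Background that tracks the vessels.** Let C and A be unrelated, each correlated ρ with B on the log scale, with equal log-SDs. The correlation of the log ratios is (1 − 2ρ)/(2 − 2ρ): 0.33 at ρ=0.25, 0 at 0.5, and −0.25 at 0.6. Simulated mean Pearson r at n=35 is 0.31, 0.00 and −0.23.

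**Partial correlation as a remedy.** Partialling on background holds the error rate near 5% when all three values are independent. At ρ=0.5 with unrelated vessels, its expected value on the log scale is −ρ²/(1 − ρ²) = −0.25/0.75 = −0.33. Simulated rank-based results at n=35 are mean r −0.29 and p<0.05 in 39%. It is therefore not a safe main analysis.

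**The case against.** The strongest reply is that the premise is not in the documents. No section says that one background serves both vessels. SAP 10.1 places the uptake data on a DMC assessment form, and SAP 6.1.2.1 refers to a DMC charter. Neither is among the documents, and either could define the background. This stands, so the size of the effect can only be conditional.

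Four stronger readings are tempting and are not supported:

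- **That the axes do share a denominator.** This is an assumption. A footnote saying so would be wrong if the backgrounds are separate.
- **That no background is measured.** The sentence on VOIs is general. It does not name the aortic arch separately either, yet the arch is analysed. A TBR cannot be formed without a background, so what is missing is the definition.
- **That the SAP tests the hypothesis with an error rate near 84%.** The planned analysis is a scatter plot. The coefficient is optional, SAP 12.2 lists Proc Corr under descriptive statistics, and Protocol 12.4 calls such analyses mainly exploratory. The 84% also needs the largest background CV tabulated and all 35 patients stenosed on one side.
- **That nobody could check.** Scans are kept as source documents, and SAP 6.1.2.2 already uses activity concentrations. The gap is in the planned listing and figures.

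The reply does not remove the mismatch between a question about uptake and outputs confined to an undefined ratio. A scatterplot with no coefficient would still show an induced slope.

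**Conclusion.** The point holds in conditional form and is worth correcting. What is certain from the text is that the hypothesis and methods speak of uptake as concentration, the six association figures show only TBR against TBR, the denominator is undefined, and the listing holds finished ratios.

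The size rests on three assumptions: a shared background, background varying independently of vessel uptake, and a background CV that the documents do not supply. Under them the artefact is negligible up to a CV of about 10%, material from about 20%, and large at 34%. Without the first it disappears, and without the second it can shrink, vanish or change sign. In every case the TBR plot cannot be interpreted without knowing the denominator. The consequence is limited to one exploratory secondary objective.

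**What to change.** - In SAP 6.1.2.3, state the TBR denominator, the VOI it comes from, and whether it is common to all vessels.
- Add each vessel's uptake and the background value to Listing 16.2.6.2.
- Beside Figures 14.2.1.5 to 14.2.1.10, add scatterplots on vessel uptake in the planned unit (%ID/g or MBq/cc). Any optional Spearman coefficient should be given on that scale too.
- Say in advance that an association counts as supported only if it is seen on both scales. Uptake alone could be correlated through background activity common to both vessels, and TBR alone through a common denominator.
- Footnote the TBR plots about the denominator only if it is in fact shared.
- A partial correlation given background may appear as one sensitivity analysis with its assumption stated, not as the main result.

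The cost is a few listing columns, up to six figures and a few lines of SAP text. The background value must already exist for TBR to be computed, so no new scans or participants are needed. The reported association may turn out weaker.
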